Study Week¹ (Days)	-4 Wks² (D-28 to D-1) Clinic	D1 Clinic	Wk 2 (D14) Telemed/ Phone Call	Wk 4 (D28) Clinic	Wk 8 (D56) Clinic or Home	Wk 12 (D84) Clinic	Wk 18 (D126) Clinic or Home	Wk 24 (D168) Clinic	Wk 28 (D196) FU ^{3/} ET ^{3,4} Clinic or Home
Vital Signs (BP, HR, RR, temp, oxygen saturation)	X	X		×	×	×	X	X	X
12-Lead ECG ¹²	X	X		×	×	×	×	X	×
Laboratory – Hematology, Coagulation ¹³ , Chemistry, urinalysis,	X	X		×	×	×	×	X	×
Columbia-Suicide Severity Rating Scale (C-SSRS)	X	X		×		×	×	X	X
Hospital Anxiety and Depression Scale (HADS)	X	X		×		×	×	X	X
Quick Inventory of Depressive Symptoms (QIDS-C)	X	X		×		×	×	X	X
Efficacy-Related Assessments									
5 TWM5	X	X		X		X		X	
Right Heart Catheterization (RHC) ¹⁴	X							X	X^{14}
Echocardiography ¹⁵	X					X		X	
WHO FC	X	X		X		X		X	
Plasma NT-proBNP level		×		×		×		×	
PAH Symptoms and Impact Questionnaire (PAH-SYMPACT)		X				×		X	
Actigraphy ¹⁶					\	$X \rightarrow$			
Pharmacokinetics									
Rodatristat PK Sampling ¹⁷		X		X		X		X	
Selexipag PK sampling ¹⁸		X		×					
Pharmacodynamics		Α		Þ		Þ		Α	
Ullile J-HIAA		< >		< >		< >		< >	
Plasma 5-HIAA ¹⁷		X		×		×		X	
Other									
Optional Blood for Future Research Sample		X						X	
Pharmacogenetic Samples		X						X	

Clinical Study Protocol Altavant Sciences GmbH

Visits at Week 2 (Telemed/Phone Call) and Week 4 (clinic visit) can occur within +/-2 days from the randomization date; Visits at Weeks 8 (Telemed/Phone call), 12 (clinic), 18 (clinic or home visit), 24 and 28/Follow Up (clinic) can occur within +/-5 days from the randomization date.

² Screening may be broken up into more than 1 visit, if necessary. Once all screening procedures are complete and the Investigator determines that the patient is eligible, the site must upload/send the required supporting documentation for approval by the Sponsor.

withdraw consent will continue to be followed for vital status from public records such as government vital statistics or obituaries, as allowed by local law, or periodic contact Patients who early terminate from the IP should be asked to return for visits as scheduled for ongoing assessments through the Week 28 Visit. Patients who withdraw consent should be asked to complete the Week 28 Visit for safety. Patients who have not completed the study as planned (through Week 24) cannot participate in OLE. Patients who (about every 6 to 12months).

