2.3. Benefit/Risk Assessment

Summaries of findings from both clinical and nonclinical studies conducted with rodatristat ethyl as well as more detailed information about the known and expected benefits and risks and reasonably expected adverse events (AEs) of rodatristat ethyl may be found in the Investigator's Brochure. This section outlines the potential adverse events of special interest (AESI; based either on preclinical or clinical data generated to date, the mechanism of action of rodatristat ethyl, or the prescribing information for telotristat ethyl [a TPH inhibitor previously approved for the treatment of carcinoid syndrome-related diarrhea] and mitigation strategies for this protocol. The potential risk for QTc prolongation (described in the Investigator's Brochure) will be further evaluated in a definitive thorough QT study in the future. Until further data are available in that regard, cardiac arrhythmia, related to an increase in QT/QTc interval, will be treated as a potential AESI and has therefore also been included in the table of potential risks below.

Although any potential benefits to patients with PAH will not be known until the study is completed, the development of a drug with disease-modifying potential will certainly be of value to patients with this diagnosis.

Potential Risk	Mitigation Stra	itegy
	Impact on Eligibility	Monitoring and Stopping Criteria OR Management Criteria
Severe constipation	None	Severe constipation (e.g., obstipation with manual evacuation indicated) and/or severe, persistent, or worsening abdominal pain would warrant withdrawal from the study.
Depression/other mood-related disturbance due to central depletion	 Exclusion of patients with active suicidal thinking or behavior at Screening/Baseline based on the Columbia-Suicide Severity Rating Scale (C-SSRS) Exclusion of patients with severe depression at Screening/Baseline based on the Quick Inventory of Depressive Symptoms Clinician-Rated (QIDS-C) or the Hospital Anxiety and Depression Scale (HADS) 	 Withdrawal of patients with: Any significant worsening on postdose C-SSRS indicative of active suicidal ideation with intent to act or suicidal behavior Severe depression or anxiety based on a HADS Depression or Anxiety Score ≥ 15 or a QIDS-C Total Score ≥ 16. Any severe psychiatric or CNS AE as determined by the Investigator.

Protocol RVT-1201-2002 Effective: 19JAN2022

Potential Risk	Mitigation Stra	ntegy

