8.1. Discontinuation of Investigational Product

The Medical Monitor should be notified of any change to background PAH therapy to determine any need for withdrawal. See Section 8.2 for study withdrawal procedures.

Patients meeting any of the following liver chemistry criteria must be withdrawn (IP should be discontinued immediately) from the study by the Investigator:

- ALT or AST > 3X ULN and TBL > 1.5X ULN or INR > 1.5
- ALT or AST > 3X ULN with the appearance of fatigue, nausea, vomiting, right upper quadrant pain or tenderness, fever, rash, and/or eosinophilia (> 5%)
- ALT or AST > 5X ULN for more than 2 weeks
- ALT or AST >8X ULN

If liver chemistry tests meet any of the above criteria, repeat testing should be performed within 48 to 72 hours and the patient followed until resolution.

Patients meeting any of the following confirmed QT/QTc-related criteria must be withdrawn from the study by the Investigator:

- QTcF interval > 500 ms
- QTcF interval > 480 ms AND increase from Baseline ≥ 60 ms
- QTcF interval > 480 ms associated with syncope, life-threatening arrhythmias, resuscitated cardiac arrest, or seizure

The Investigator must also discontinue/withdraw a patient's participation in the study if any of the following criteria apply:

- Pregnancy
- Significant protocol violation/lack of compliance with the study and/or study procedures non-compliance with IP for discontinuation of patient is defined as < 50%.
- Severe constipation (e.g., obstipation with manual evacuation indicated) and/or severe, persistent, or worsening abdominal pain
- Any significant worsening on postdose C-SSRS indicative of active suicidal ideation with intent to act (defined as C-SSRS Suicidal Ideation category score of 4 or 5) or behavior (either preparatory acts/behavior, aborted attempt, interrupted attempt, or actual attempt)
- Severe depression or anxiety based on a HADS Depression or Anxiety score ≥ 15, or a QIDS-C Total Score ≥ 16.

• Any severe psychiatric or CNS AE as determined by the Investigator.

The Investigator may discontinue/withdraw a study patient's participation in the study if any of the following criteria apply:

Protocol RVT-1201-2002

Effective: 19JAN2022

• Behavioral or administrative reason

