8.2.1. Investigational Product Discontinuation

If a patient is permanently discontinued from the IP, but agrees to study visits, the patient will come in for the Early Termination Visit and continue attending clinic visits as scheduled through the 24-week visit (from first dose). A final follow-up visit will not be required.

If a patient prematurely discontinues IP prior to the Week 24 Visit, the Investigator will make every attempt to perform a RHC, as clinically feasible, prior to or within 7 days of IP discontinuation (but after at least 12 weeks of IP), and prior to initiation of any new PAH medications.

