9.2.8. Suicidal Ideation and Behavior Risk Monitoring

Rodatristat ethyl acts to decrease peripheral 5-HT levels and it was designed to not cross the blood-brain barrier; therefore, CNS 5-HT levels are not expected to be significantly impacted. However, patients being treated with IP should be monitored appropriately and observed closely for suicidal ideation and behavior or any other unusual changes in behavior, especially at the beginning and end of the course of treatment, or at the time of dose changes, either increases or decreases. IP in patients who experience signs of suicidal ideation or behavior following a risk assessment (see Section 8.1) must be stopped.

Screening and Baseline assessments (within 1 month) of suicidal ideation and behavior as well as potential treatment-emergent suicidal ideation and behavior will be monitored during the study using the C-SSRS.

Suicidal ideation and behavior as well as mood and anxiety assessments, as detailed below, will be obtained at time points indicated in the SoA in (Section 1.3).

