APPENDIX 3. LIVER SAFETY: SUGGESTED ACTIONS AND FOLLOW-UP ASSESSMENTS

Protocol RVT-1201-2002

CTCAE Grade	Description	IP	Symptom/treatment
Mild = 1	AST or ALT > 1.5X ULN < 3X ULN	Continue as planned	No action taken
Moderate = 2	AST or ALT ≥ 3X ULN and < 5X ULN and no signs of severe liver damage	Reduce to one pill BID or interrupt treatment (to be decided by Investigator, based on individual risk assessment.)	Re-test ALT and AST, as well as ALP, TBL, and eosinophils within 48-72 hours, then at ~7 days, then at ~2 weeks, and assess for signs of severe liver damage: If AST and ALT < 3X ULN after 2 weeks, return to initial dose if reduced, restart at reduced dose if interrupted. Monitor labs (see above) every 2 weeks for at least 8 weeks. If AST and ALT ≥ 3X ULN after 2 weeks or anytime thereafter, permanently discontinue study medication.
Severe = 3	AST or ALT increase to ≥ 5X ULN and < 8X ULN and no signs of severe liver damage	Interrupt treatment	Re-test ALT and AST, as well as ALP, TBL, and eosinophils within 48-72 hours, then at ~7 days, then at ~2 weeks, and assess for signs of severe liver damage: • If AST and ALT < 3X ULN after 2 weeks, restart at reduced dose. Monitor labs (see above) every week for 4 weeks, then

Protocol RVT-1201-2002 Effective: 19JAN2022

CTCAE Grade	Description	IP	Symptom/treatment
			every 2 weeks for at least 8 weeks.
			• If AST and ALT ≥ 3X ULN after 2 weeks or anytime thereafter, permanently discontinue study medication.
Life-threatening = 4	AST or ALT increase to ≥ 8X ULN or signs of severe liver damage:	Permanently Discontinue	Patients showing these laboratory abnormalities need to be followed up
	-Increase of liver transaminases (ALT or AST ≥ 3X ULN)		closely
	and		
	Appearance of fatigue, nausea, vomiting, right upper abdominal quadrant pain or tenderness, fever, rash and/or eosinophilia (> 5%)		
	or		
	TBL > 1.5X ULN		
	or		
	INR > 1.5		

Abbreviations: ALP = alkaline phosphatase; ALT = alanine aminotransferase; AST = aspartate aminotransferase; BID = twice daily; CTCAE = Common Terminology Criteria for Adverse Events; INR = international normalized ratio; IP = investigational product; ULN = upper limit of normal

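### Protocol 8.1 literally withdraws patients from the study at its safety criteria, while the rest of the protocol only stops IP and keeps follow-up; a stop before Week 12 can then leave no PVR

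*Protocol*

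**What the plan says.** Protocol 8.1 is headed as a section on discontinuing IP, but its operative words concern the study. Patients meeting the liver criteria "must be withdrawn (IP should be discontinued immediately) from the study by the Investigator". The QTcF criteria also require withdrawal from the study. A further list requires the investigator to end participation for severe constipation or abdominal pain, worsening on the C-SSRS, severe HADS or QIDS-C scores, and severe psychiatric or CNS events. In the 2.3 risk table, the severe-constipation line agrees: such an event "would warrant withdrawal from the study".

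Other current text treats these events as a reason to stop the drug:

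- **4.4.1.2:** if the Section 8 criteria are met, IP is permanently discontinued. Study withdrawal is not mentioned.
- **9.2.8:** "IP in patients who experience signs of suicidal ideation or behavior following a risk assessment (see Section 8.1) must be stopped".
- **Appendix 3, Grade 4 liver:** IP is permanently discontinued, and "Patients showing these laboratory abnormalities need to be followed up" closely.
- **8.2.1:** a patient permanently off IP who agrees to visits keeps attending through Week 24. It then adds "A final follow-up visit will not be required".
- **1.3 Schedule of Assessments, footnote 3:** patients who stop IP early "should be asked to return for visits as scheduled for ongoing assessments through the Week 28 Visit".
- **Section 8, opening sentence:** unnecessary withdrawal is to be avoided and patients retained.

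On the primary endpoint, footnote 14 and 8.2.1 ask for an RHC at early termination only from Week 12 on. SAP 7 makes ITT the primary population. SAP 7.1.2.2 gives a PVR missing for tolerability the worst value in the planned arm.

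**The concern.** For the same event, a site can read one instruction to end study participation and another to stop the drug and keep the visits. Both cannot be followed. A site obeying 8.1 before Week 12 loses the only planned post-baseline RHC, the one at Week 24. Under 8.2.1 the same patient, if willing, would still have it.

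The patients affected are those stopped for tolerability. Their missing PVR is the kind that the SAP replaces with the arm's worst value. If such stops were commoner on active drug, the estimated effect would shrink because of an imputed number where a measurement could have been obtained.

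There is also a safety side. The liver, constipation and psychiatric events are adverse events of special interest, which 9.3.4 says are to be followed to resolution or stabilization. Ending participation works against that. In addition, the 8.2.1 waiver of a final visit conflicts with footnote 3 and with the 4-week follow-up period in 4.1.

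**Working it through.** **1. Which patients lose a PVR**

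| Time of stop | 8.1 read literally | 8.2.1 / footnote 3 |
|---|---|---|
| Before Week 12 | No RHC planned after baseline | Scheduled Week 24 RHC, if the patient agrees |
| Week 12 or later | RHC requested at early termination | RHC requested at stopping, then the Week 24 RHC |

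The gap is therefore confined to stops before Week 12, plus later stops where the requested RHC is not done.

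**2. The plan's own power figure**

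Inputs (Protocol 10.2, SAP 3): 30 per arm, difference 18, SD 24, two-sided 0.05. The noncentrality is 18 / (24 × √(2/30)) = 2.90. The two-sample t-test then has 81.5% power, which agrees with the stated figure of at least 80%.

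**3. Effect of worst-value imputation**

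The documents give no rate for these stops, and 8.2 calls withdrawal uncommon. The number m of stopped patients out of 30 is therefore an assumption. The model is an unadjusted t-test on normal data. The worst value is the maximum among the arm's observed patients, and a patient measured off drug is assumed to sit at the placebo mean.

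- Not measured, active stops only: difference = 18 − (m/30) × 24 × E[maximum of 30 − m standard normals]. For m = 1, 2, 3, the term 24 × E[max] is 48.7, 48.3 and 48.0.
- All measured off drug: difference = 18 − (m/30) × 18.

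| Stops, active / placebo | None measured | All measured |
|---|---|---|
| 0 / 0 | 18.0 (power 81%) | 18.0 (81%) |
| 1 / 0 | 18 − 1.6 = 16.4 (72%) | 18 − 0.6 = 17.4 (79%) |
| 2 / 0 | 18 − 3.2 = 14.8 (61%) | 18 − 1.2 = 16.8 (75%) |
| 3 / 0 | 18 − 4.8 = 13.2 (50%) | 18 − 1.8 = 16.2 (72%) |
| 2 / 1 | 18 − 3.2 + 1.6 = 16.4 | 16.8 |
| 3 / 2 | 18 − 4.8 + 3.2 = 16.4 | 16.2 |
| 3 / 3 | 18 − 4.8 + 4.8 = 18.0 (72%) | 16.2 (72%) |

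Powers are from simulation. The avoidable part is the gap between the two columns: 1.0, 2.0 and 3.0 points in the active-only rows, 0.4 at 2/1, and none at 3/2 or 3/3. For 3/0 with 0, 1, 2 or 3 of the three measured, the difference is 13.2, 14.1, 15.1 or 16.2. If nobody is measured, nothing is recovered.

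**4. The follow-up gap in 8.2.1**

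SAP 8.2 counts treatment-emergent events up to 28 days after the last dose for patients who do not enter the OLE. Under 8.2.1 the last visit is Week 24 (Day 168). A last dose on Day 141 or later gives 168 − 141 = 27 days or fewer, which is inside the window. Under footnote 3 the last visit is Week 28 (Day 196). Even a last dose on the evening of Day 167 then has 196 − 167 = 29 days. These are nominal days, and the visit window is plus or minus 5 days.

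**The case against.** The strongest reply is that the documents largely settle the reading. Section 4.4.1.2 construes the Section 8 criteria as a drug stop. The section opens with a retention instruction, and 8.1 is headed as IP discontinuation. Its liver block asks for follow-up to resolution, and 8.1 points onward ("See Section 8.2 for study withdrawal procedures") to a section that contains 8.2.1. That section makes no exception for the 8.1 criteria. This stands as evidence of intent. A reader might infer that the sponsor deliberately chose study withdrawal, and the documents do not support that inference. The conflict is still not harmless, because a site acts on the instruction in front of it.

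A second reply concerns size. A reader might take from the 3/0 row that power falls to 50%. Nothing in the documents supports 3 active stops before Week 12 with none on placebo. The HADS, QIDS-C, abdominal pain and liver criteria can all be met on placebo. This objection stands, and the figures are bounds under an assumption.

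Third, worst-value imputation and off-drug measurement answer different questions, and the SAP chose to score tolerability loss as a poor outcome. That is fair. The blinded intercurrent-event meeting (SAP 7.1.2.1) and the observed-case analysis (7.1.2.4) also limit or reveal the influence. They cannot recover a measurement that was never taken.

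**Conclusion.** The contradiction in the current text is certain and should be corrected. An IP stop with continued follow-up is very probably what was meant, so this is a wording error in a mandatory instruction.

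Its effect on the primary endpoint is conditional. It needs a site that follows 8.1 literally, a stop before Week 12 (or a later one without the requested RHC), and a patient who would otherwise have agreed to the Week 24 RHC. Bias against the drug also needs more such stops on active drug than on placebo. If all of this holds for 1 to 3 of 30 patients, the avoidable attenuation is at most about 1 to 3 points of 18. With similar numbers in each arm it is small or nil. The 2/1 and 3/2 rows give mean differences only; the imputed extremes also widen the spread, so power should not be read off them.

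The follow-up gap in 8.2.1 does not rest on any assumed imbalance, but it is limited. It affects patients who stop in about the last 4 weeks at sites that apply the waiver in place of footnote 3. It would be too much to say that post-treatment safety follow-up is missing, since 4.1 and footnote 3 provide it.

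**What to change.** - **8.1 and 2.3:** for the liver, QTcF, severe constipation or abdominal pain, and psychiatric criteria, replace study withdrawal with permanent discontinuation of IP, followed by 8.2.1. Scheduled visits and the Week 24 RHC continue where feasible and where the patient agrees. Change no stopping threshold. Keep study withdrawal for pregnancy, as Appendix 4 requires.
- **8.2.1:** delete the sentence waiving the final follow-up visit, and align the section with footnote 3, with visits through Week 28. A rule of Week 24 or 4 weeks after the last dose, whichever is later, would be worse: it would shorten footnote 3's follow-up for early stoppers.
- **7.7:** state that patients permanently stopped under the 8.1 safety criteria cannot enter the OLE. Once retained to Week 24, they could otherwise meet the completion tests in footnote 4 and in OLE inclusion criterion 1. Section 7.4 does limit rollover to patients who do not discontinue prematurely, but 7.7 contains no explicit exclusion.

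No change to RHC selection in SAP 4.7.1 is recommended. Choosing between an RHC at stopping and an off-drug Week 24 RHC is an estimand decision for the sponsor.

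The cost is a wording amendment with IRB/IEC approval. Patients stopped early would contribute some off-drug Week 24 PVR values, and those whom a site would have withdrawn under the literal wording would be asked for an RHC that they would otherwise not have had.

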8.1.1. Temporary Discontinuation

Temporary discontinuation of IP of up to 7 days will be allowed for extenuating circumstances or to manage AEs.

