4.4. Dose Adjustment Criteria

4.4.1. Dose Reduction

All determinations of rodatristat ethyl dose reduction should be discussed with the Medical Monitor prior to implementing unless time does not allow for safety.

Temporary dosage reductions or discontinuations will be allowed to manage AEs/AESIs (or other instances to be discussed with the Medical Monitor), including gastrointestinal AEs (e.g., diarrhea, nausea, or vomiting) or liver enzyme increase occurring during the 24 weeks of the study. Judicious use of antidiarrheal and/or anti-emetic medications will be permitted. One level of dose reduction is available.

To reduce the IP, the patient will be instructed to take one tablet in the morning and one tablet in the evening from the appropriate dispensed bottles during the dose reduction period per dosing instructions supplied in a separate document. If AEs continue, the patient may stop taking the IP completely for up to 7 days before restarting.

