4.4.1.2. Aminotransferase (Alanine aminotransferase or Aspartate Aminotransferase) Elevation

Management recommendations for ALT or AST elevations are based on U.S. Food and Drug Administration (FDA) Guidance for Liver Toxicity.

In general, all baseline or treatment-emergent ALT or AST elevations > 3X ULN should be confirmed within 48 to 72 hours with repeat assessments of ALT and AST as well as TBL, alkaline phosphatase (ALP), prothrombin time/INR, and complete blood count for eosinophil levels. Further details for managing IP reduction, restart, and discontinuation can be found in Appendix 3.

If at any time, the criteria as outlined in Section 8 are met, the IP must be permanently discontinued.

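### Section 8.1.1 caps temporary interruption at 7 days without exception, but Appendix 3 lets interrupted ALT/AST cases restart only after a 2-week re-test

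*Protocol*

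**What the plan says.** Protocol Section 8.1.1 consists of one sentence: "Temporary discontinuation of IP of up to 7 days will be allowed for extenuating circumstances or to manage AEs". It names no organ system, grade or exception.

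Appendix 3 sets out what to do when aminotransferases rise. Its Grade 3 row covers "AST or ALT increase to ≥ 5X ULN and < 8X ULN and no signs of severe liver damage". The only action it lists for study drug is to interrupt. ALT and AST are repeated within 48 to 72 hours, "then at ~7 days, then at ~2 weeks, and assess for signs of severe liver damage". The restart rule is "If AST and ALT < 3X ULN after 2 weeks, restart at reduced dose". If the enzymes are still at or above 3 times ULN at that point, or at any time afterwards, study drug stops for good.

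The Grade 2 row (at least 3 and below 5 times ULN) gives the Investigator a choice: "Reduce to one pill BID or interrupt treatment (to be decided by Investigator, based on individual risk assessment". The re-test schedule is the same. If both enzymes are below 3 times ULN after 2 weeks, the instruction is to "return to initial dose if reduced, restart at reduced dose if interrupted".

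Two other places bear on the point. Section 4.4.1.2, on aminotransferase elevation, says "Further details for managing IP reduction, restart, and discontinuation can be found in Appendix 3". Section 4.4.1, on dose reduction, says "If AEs continue, the patient may stop taking the IP completely for up to 7 days before restarting".

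**The concern.** The two rules give different maximum lengths for the same action. An ALT or AST elevation managed by stopping drug is an adverse event managed by temporary discontinuation, so it falls within the wording of 8.1.1. Section 4.4.1 also lists liver enzyme increases among the events that temporary reduction or discontinuation is meant to manage.

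A site that took 8.1.1 as binding would have two options. It could restart by day 7, before the re-test on which Appendix 3 bases the decision. Or it could treat day 7 as the end of any permitted interruption and lose a restart that Appendix 3 allows. A site that followed Appendix 3 would exceed the 8.1.1 limit and might have to record a deviation for doing so. Hepatic enzyme elevation is listed as an adverse event of special interest in Section 9.3.1 and has its own mitigation row in the benefit/risk table of Section 2.3. The restart instruction for it should have only one reading.

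**Working it through.** This is a comparison of two stated durations; no power or sample-size figure is involved.

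**Inputs**
- Longest temporary discontinuation: 7 days (Section 8.1.1).
- Re-tests after a Grade 2 or Grade 3 elevation: 48–72 hours, about 7 days, about 2 weeks (Appendix 3).
- Restart condition after an interruption: both enzymes below 3 times ULN after 2 weeks (Appendix 3, both grades).

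**Step 1: length of an interruption that ends in restart.** The restart condition is tied to the 2-week point and to no earlier test. Two weeks = 2 × 7 = 14 days. Excess over the cap: 14 − 7 = 7 days, so the interruption is twice the permitted length.

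**Step 2: what is known by day 7.** At most two of the three scheduled re-tests (48–72 hours and about 7 days) can have been done. The third, which decides restart, cannot.

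**Step 3: sensitivity to when the clock starts.** Suppose the site keeps dosing until the 48–72 hour re-test confirms the elevation, and the 2 weeks run from the first raised value. Time off drug is then 14 − 3 = 11 to 14 − 2 = 12 days, still above 7. To fit the cap, dosing would have to continue for 14 − 7 = 7 days after the first raised value, which defeats an instruction to interrupt.

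**Step 4: which patients meet the conflict**

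| Situation | Appendix 3 action | Compatible with 8.1.1? |
|---|---|---|
| Grade 2, dose reduced | One tablet twice daily | Yes; drug is not stopped |
| Grade 2, interrupted, recovers to below 3 times ULN | Restart at reduced dose after 2 weeks | No; about 14 days |
| Grade 3, recovers to below 3 times ULN | Restart at reduced dose after 2 weeks | No; about 14 days |
| Grade 2 or 3, not recovered at 2 weeks | Permanent discontinuation | Not a temporary stop in the end |
| Grade 4 | Permanent discontinuation | Not applicable |

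For Grade 3 the site has no route that satisfies both rules and still ends in restart.

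**Step 5: whether any text ranks the rules.** Section 4.4.1.2 points to Appendix 3 for further detail. It does not mention the 7-day limit or say that Appendix 3 overrides it, and 8.1.1 does not refer to Appendix 3.

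**The case against.** The best answer is that a specific rule governs a general one. Section 8.1.1 is a single general sentence, whereas 4.4.1.2 is written for ALT/AST and refers restart decisions to Appendix 3; Section 9.3.1 points there too. Other parts of the protocol also do not treat 7 days as universal. Appendix 2 interrupts for diarrhea until recovery to Grade 1 or lower, with no time limit. Section 8.1 withdraws a patient for values above 5 times ULN only after more than 2 weeks. Dose reductions are to be discussed with the Medical Monitor and safety concerns with the Sponsor, so an early restart would probably be caught. All of this stands, and it makes the practical risk small. It does not remove the conflict: the precedence has to be inferred, and the title of Appendix 3 calls its contents suggested actions, which lets a reader rank the body text above it.

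Three stronger readings are tempting, and the documents do not support them.

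- *The protocol instructs sites to re-expose patients at day 7.* It does not. Section 8.1.1 is permissive and attaches no consequence to passing day 7: neither restart nor withdrawal.
- *Section 4.4.1 is a second contradiction.* Its 7-day sentence is a conditional step for events that continue after a dose reduction. Grade 3 goes straight to interruption and skips that step. It is relevant only as a place for a matching edit.
- *The longer interruption damages compliance or the efficacy analysis.* Nothing shows that. The SAP's actual-compliance measure (Section 8.1), which feeds the Per Protocol set, is designed to account for interruptions and reductions. The Treatment Completer set excludes any interruption whatever its length.

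**Conclusion.** The inconsistency is real and narrow. For Grade 3 ALT/AST elevations that recover, and for Grade 2 elevations that the Investigator chooses to interrupt and that recover, the Appendix 3 restart comes at about 14 days against a cap of 7. Both rules cannot be met.

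The conclusion rests on two readings: that an ALT/AST interruption is a temporary discontinuation to manage an adverse event, and that the 2 weeks run from about the time drug is stopped. Step 3 shows that a few days' shift in the second does not change the result.

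The number of patients affected cannot be derived from the documents and is probably low. Section 4.7 reports mild, transient ALT elevations in 5 of 136 healthy subjects (3.7%), none described as reaching the Grade 3 range; patients with PAH on background therapy may differ. Most sites would probably follow Appendix 3. The case for correction is that the text concerns re-exposure after a named safety event and the remedy is small. No effect on the efficacy analysis, sample size or power is claimed.

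**What to change.** Amend Section 8.1.1, and for consistency the 7-day sentence in Section 4.4.1, to read along these lines: *up to 7 days, except where Appendix 2 (diarrhea) or Appendix 3 (ALT/AST) specifies the interruption and restart criteria; for ALT/AST elevations IP must not be restarted before the 2-week re-test required by Appendix 3.*

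The exception should name both appendices. One limited to liver events would imply that the 7-day cap does bind Appendix 2 diarrhea interruptions, which run to recovery with no stated limit, and would sharpen a parallel mismatch.

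The cost is one clause in two sections, with no added visits, tests or patients. Under Appendix 5 an amendment needs IRB/IEC approval, here across the 17 countries in the synopsis, so the change is best bundled with the next amendment, with a clarification letter to sites in the meantime. It remains useful after Week 24, because Section 7.12 carries the Section 8 criteria for stopping study drug into the open-label extension, which may run 6.5 years.
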